6.1.1.1 Educational Sessions

The education portion will comprise of 10 separate weekly lectures, lasting approximately 1 hour. Sessions will be conducted by credentialed RMD staff members and participants in both the CON and AET+ arm will receive the same educational lectures remotely within the 10-week intervention period. Educational topics to be covered will be related to exercise programming, safety and well-being such as considerations for benefits and adaptations of exercise, relevant anatomy and physiology, nutrition and lifestyle considerations, managing co-morbid conditions, forms of exercise training, home recommendations, and locating community resources.

6.1.1.2 Aerobic Exercise Training Sessions

The AET regimen will consist of 10 weeks of aerobic exercise. Vital signs and review of cardiac-related signs or emerging symptoms will be performed before and after every session. Following a brief warm-up period, participants will be encouraged to target 30 minutes of aerobic exercise, followed by a brief cool-down. The sessions will be continuous unless the participant cannot tolerate the regimen, in which case the exercise bouts will be alternated with rest intervals until the total time of the exercise bouts equals the 30 minutes. The intensity of exercise will be guided using heart rate (HR), and gradually increased from light-moderate to moderate-high intensity as safely tolerated by the participant.

The frequency of the sessions will be 3 times per week, unless make up sessions are needed in the 10 weeks. The target endpoint for each session will be completion of the prescribed training time, however symptomatic endpoints for stopping the training session will be those recommended by the ACSM, or as needed for the safe management of participants.

For participants in the AET+ group, the exercise sessions will be conducted as out-patient visits to the NIH CC under direct supervision by credentialed RMD staff members. To explore and collect pilot feasibility data for conducting remote monitoring of exercise sessions, participants in the CON group may perform the exercise sessions outside NIH with real-time remote supervision by credentialed RMD staff members. It is anticipated that some participants may need to perform initial exercise sessions as out-patient visits to the NIH CC for familiarization and safe exercise participation. Other participants may be deemed unsuitable for remote monitoring due to safety concerns (e.g., no suitable exercise space, high risk of injury from falls, unwilling or unable to perform glucose monitoring, demonstrate impulsive or unsafe behaviors, or lack the technologic skills, connectivity, or bandwidth required for remote monitoring) or refusal. There may also be participants that prefer or opt to perform the exercise sessions on-site at NIH. Participants will be provided and taught how to use the necessary equipment (e.g., pulse oximetry, blood pressure monitor, HR monitor, tablet, etc.) to enable vital sign measurement and remote monitoring of sessions off-site. Additional precautions that will be taken for participants exercising off-site include reviewing and identifying common trip hazards at the remote site,

requesting an open and flat space for conducting the exercise sessions and confirming their location, contact information and presence of any other person(s) prior to the start of all sessions. The credentialed RMD staff member conducting the session will review all this information prior to the start of all sessions and have the participants' medical history immediately available during the session.

6.2 MEASURES TO MINIMIZE BIAS: RANDOMIZATION AND BLINDING

Participants will be randomized to either education (CON arm) or exercise + education (AET+ arm). Due to the nature of the intervention, participants will not be blinded to their treatment allocation. Study personnel will be blinded through initial baseline screening/testing and randomization, however following randomization, due to the nature of exercise training and the time points involved in this study, the blinding process will no longer be possible.

We will use random block-size randomization (with block sizes randomly varying between 4 and 6) to keep groups as equal in number as possible and to avoid early filling of one of the groups. To minimize bias, an independent randomizer who is not affiliated with this study in any other way, will perform randomization of participants.

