	Intervention Period 1 Week 3 +/- 1 week	Study Visit 2 (10-week follow-up) Week 14 +/- 4 weeks	Intervention Period 2 Week 18 +/- 1 week	Study Visit 3 (20-week follow-up) Week 29 +/- 4 weeks	3-month follow-up 1 Week 45 +/- 1 week	3-month follow-up 2 Week 58 +/- 1 week	3-month follow-up 3 Week 71 +/- 1 week	3-month follow-up 4 Week 84 +/- 1 week
Procedures								
History and Physical Exam, Cardiology Evaluation		X		X				
Concomitant medication review		X		X				
Vital signs		X	X	X				
ECG, Echo, PFT, Chest CT, Neuromuscular Ultrasound		X		X				
Biospecimen Collection (blood and urine) ^a		X		X				
Physical Assessment (6MWT, SPPB/MiniBEST, CPET)		X		X				
VAS-CFS and Qualitative Interviews ^b		X		X				
Patient-reported Outcomes and QOL		X		X	X	X	X	X
Physical activity and sleep quality monitoring	X	X	X	X	X	X	X	X
Other assessments (e.g. neurology, vascular function)		X		X				
Optional assessment (skin biopsies)		X		X				
Supervised Exercise Session (thrice weekly)			X					
Education Sessions (weekly)	X							
Adverse event review and evaluation	X	-----	-----	-----	-----	-----	-----	X
Complete Case Report Forms (CRFs)	X	-----	-----	-----	-----	-----	-----	X
^a Including urine pregnancy test (women of childbearing potential); ^b Repeated before and up to 72 hours after the CPET								

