The treadmill is equipped with handrails for aiding balance and providing increased stability. The treadmill also is equipped with a “hot” switch that is easily within the reach of the participant while walking on the treadmill. When the switch is activated, the treadmill stops and ends the test immediately. Under this circumstance, the treadmill cannot be restarted unless both the treadmill itself and the computer control are reset. Participants are instructed in treadmill safety and the use of the hot switch before beginning the test protocol. Participant response to the test is monitored visually, electronically, and by verbal interaction between the participant and the testing staff.

Participants with diabetes will be monitored before and after exercise testing for glucose levels and glycemic responses to exercise. Physical activity generally reduces glycemic levels and intense activity can cause transient blood glucose derangements in individuals with diabetes.

Thus, the risks of hypoglycemia and hyperglycemia are associated with exercise in individuals with diabetes. The acute risks of exercise for individuals with diabetes must be weighed against the potential long-term benefits such as a reduction in cardiovascular disease risk and improved hemodynamic function. In order to reduce risks and avoid the onset of diabetic symptoms during participation in the study, glucose monitoring will be performed per standard of care.

2.3.1.9 6 Minute Walk Test (6MWT)

The major risks associated with this test are stumbles and falls, which could result in sprains, strains, fractures, contusions, and concussion. Additional risks include heart attack, cardiac arrest and sudden death similar to the CPET.

To maintain participant safety during this test, the 6MWT will be conducted by credentialed RMD staff members with expertise in exercise testing. Participants will be screened for evidence of pre-existing cardiovascular disease and subsequently monitored for the development of signs and symptoms that could indicate complications such as hypoxia, chest pain, shortness of breath, nausea, pallor and diaphoresis. Additionally, they will be instructed to sit immediately following the test to avoid falling in the event they should become dizzy after strenuous exercise.

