4 STUDY DESIGN

4.1 OVERALL DESIGN

This is a single-site randomized controlled trial with a wait-list (cross-over) design. The study will be led by the Rehabilitation Medicine Department (RMD) at the NIH Clinical Center, in collaboration with other NIH institutes. An overview of the study is as follows:

The overall aim of this RCT is to determine whether AET is beneficial for improving functional outcomes and recovery among survivors of COVID-19. All participants will perform baseline assessments (Study visit 1) including physical, cognitive testing, patient-reported outcomes, and vascular function as listed in **Section 8, Study Assessments and Procedures**. Thereafter, participants will be randomized to either one of 2 arms for 10 weeks: 1) an aerobic exercise training with education (AET+) group, or 2) a wait-list control group (CON) provided with education only. After 10 weeks, both groups will repeat the same assessments as performed at baseline (Study Visit 2; 10-week follow-up). Following this visit, participants in the CON group will crossover and perform 10 weeks of AET either on-site or remotely, followed by a third assessment visit (Study Visit #3; 20-week follow-up). Participants will also begin wearing a wristwatch accelerometer at the baseline study visit and through to the follow-up time point (10 weeks for AET+, 20 weeks for CON), for continuous collection of free-living physical activity and sleep quality. In addition, all participants will be monitored periodically over one year to capture physical activity, sleep quality and health-related QOL outcomes over time.

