8.3.5.3 Cardiopulmonary Exercise Test (CPET)

The CPET will be obtained at every study visit. Participants will complete an incremental ramp protocol on the treadmill or cycle ergometer where the work rate will be gradually increased until volitional fatigue is reached by the participant. The ramp rate used will be based on participants' responses to their current physical activity habits. Participants will perform the CPET on room air, unless they were prescribed O₂, in which case, supplemental O₂ will be provided during the test using the same delivery device and flow at each test to maintain consistency. Rating of perceived dyspnea and rating of perceived exertion will be asked and recorded throughout the test.

This is a symptom-limited test in which the target endpoint is exertional intolerance defined as the participants expressed desire to stop exercising despite strong verbal encouragement from the testing staff. Other symptomatic endpoints for stopping the exercise test will be those recommended by the ACSM. Additionally, should any participant's O₂ saturation decrease to <80%, the test will be terminated with or without the presence of symptoms of severe dyspnea. Blood glucose of diabetic participants will be monitored before and after testing, and as clinically necessary. Testing will be performed by qualified staff using an NIH glucometer.

The CPET will be performed on a treadmill or cycle ergometer interfaced with the Medgraphics Cardio2 Ultima® CPX system for automatic increment of the work rate. A facemask placed over the lower portion of the participant's face (mouth and nose) or a mouthpiece and nose-clip will house the interface for pulmonary gas exchange measurements. For participants prescribed O₂, this test may be performed without collecting gas exchange as modified oxygenation may produce inaccurate gas exchange variables ([121](#)). Heart rate will be obtained in all participants from ECG recordings and electrodes will be placed on the participants' chests in the standard Mason-Likar exercise testing configuration. ECG will be monitored and recorded continuously throughout the test and recovery.

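### Section 6.2 gives no reason that requires an unmasked tester at Visit 2, and no rule stops a participant's own trainer from running that participant's primary walk test

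*Combined protocol and SAP*

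**What the plan says.** Section 6.2 states that "participants will not be blinded to their treatment allocation". It then says "Study personnel will be blinded through initial baseline screening/testing and randomization", and that afterwards "due to the nature of exercise training and the time points involved in this study, the blinding process will no longer be possible". No masked outcome assessor and no separation of trainers from testers is described anywhere else in the protocol.

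The staffing text uses one category for every role. Section 2.3.1.9 says that "the 6MWT will be conducted by credentialed RMD staff members with expertise in exercise testing". Section 2.3.3 gives monitoring of the CPET to the same category of staff. Section 6.1.1.2 puts the on-site AET+ sessions "under direct supervision by credentialed RMD staff members".

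The Schedule of Activities (Section 1.3) has the same column heading in the AET+ and CON tables: "Study Visit 2 (10-week follow-up) Week 14 +/- 4 weeks". Section 4.1 has both groups repeat the baseline assessments at that visit, with CON crossing over to exercise only afterwards.

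**The concern.** Before randomisation there is no allocation to know, so masking of personnel that ends at randomisation protects the baseline tests but not the outcome. The outcome tests depend on effort. The 6MWT (Section 8.3.5.1) asks for as much distance as the participant can cover at a self-chosen pace. The CPET (Section 8.3.5.3) ends on the participant's "expressed desire to stop exercising despite strong verbal encouragement from the testing staff", and its time to exhaustion is a named supporting measure of physical function in Section 3.

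By Visit 2 an AET+ participant may have had up to 30 supervised on-site sessions (3 a week for 10 weeks), while a CON participant has had remote lectures only. The trial's hypothesis favours exercise. If the tester knows the arm, or is the participant's own trainer, tester expectation and familiarity could add a between-arm difference that is not a training effect. Neither baseline adjustment nor a larger sample would remove it.

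**Working it through.** **1. Do the two stated reasons apply at Visit 2?**

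- *Time points.* The window (week 14 ± 4 weeks), the test list and the position before crossover are the same in both arms, so the calendar does not reveal the arm at Visit 2. It does at Visit 3, which only CON attends, but Visit 3 does not enter the primary ANCOVA in Section 9.4.2.
- *Nature of exercise training.* This unblinds the participant and whoever supervises the sessions. It does not by itself unblind a tester who did not supervise them and was not told the allocation.

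**2. Inputs for an illustration of size.** Section 9.2 gives SDs of 98.6 m (control) and 71.3 m (exercise), an expected difference of 56.7 m, a significance level of 0.05, 80% power, 38 per group, and a two-sample t-test with unequal variance. Section 3 sets the minimal important difference at 30 m.

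**3. The plan's own figure reproduces.** The unequal-variance t-test at two-sided 0.05 gives power of 79.8% with 37 per group and 80.8% with 38. One-sided testing would need only 30, so the stated 38 is two-sided. Allowing for 85% completion, 76 / 0.85 = 89.4, which rounds up to 90 randomised.

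**4. Standard error at 38 per group.** SE = √((98.6² + 71.3²)/38) = √(14,805.65/38) = 19.74 m. With 67.4 degrees of freedom the critical t is 1.996, so the smallest significant difference is 1.996 × 19.74 = 39.4 m.

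**5. False-positive rate under an assumed bias.** The documents give no size for tester bias; the values of b below are assumptions. With no true effect and a bias of b metres favouring AET+, the rejection rate is P(T > 1.996) + P(T < −1.996), where T is non-central t with 67.4 degrees of freedom and non-centrality b/SE. The last column also assumes that ANCOVA lowers the SE by 20%.

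| Assumed bias b | b as share of 56.7 m | b/SE | Rate, SE 19.74 m | Rate, SE 20% lower |
|---|---|---|---|---|
| 5 m | 9% | 0.25 | 5.7% | 6.1% |
| 10 m | 18% | 0.51 | 7.9% | 9.6% |
| 20 m | 35% | 1.01 | 17.0% | 23.9% |

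A more precise analysis makes a fixed bias matter more. Masking the tester changes no design figure: the sample size stays at 38 per group and 90 randomised.

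**The case against.** Several counter-arguments are sound and set the limits of the point.

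- *A reader might infer that the schedule contradicts Section 6.2 outright.* It does not. The time-point reason is valid for Visit 3, and the exercise-training reason is valid for participants and trainers. AET+ participants also come on site three times a week, so RMD staff may recognise them whatever the visit calendar says.
- *A reader might infer that trainers will test their own trainees.* The documents name a department and a credential, not individuals. They are silent on the matter; they do not plan it.
- *The encouragement wording belongs to the CPET.* The 6MWT uses standardised instructions, a pre-measured course and published stopping rules (Section 8.3.5.1). These limit tester influence on the primary outcome without removing it.
- *Masking may leak.* Participants may disclose their arm. Section 10.6 has research staff meet regularly during the intervention to discuss each participant, and a tester who attends could learn the allocation there.
- *Masking of readings is partly in place.* Section 10.8.1 already puts files under a participant code and transcripts under a number, although investigators hold the key and a transcript's content can reveal the arm. The documents do not say whether image readers know the arm. Accelerometer outcomes come from established equations (Section 8.3.9), so masking a scorer there would add little.

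What stands is narrower: at Visit 2 nothing in the documents requires an unmasked tester, and nothing separates tester from trainer.

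**Conclusion.** The point holds for the Visit 2 6MWT and CPET. Section 6.2 gives up all personnel masking after randomisation, yet neither of its reasons requires that at the primary time point.

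The size of any resulting bias is unknown. The rise from 5% to about 6% to 17% illustrates how sensitive the primary test would be. It rests on assumed biases of 5 to 20 m, no true effect and the unadjusted SE of 19.7 m. A reader might take it as evidence that the trial's error rate is inflated by that amount; the documents do not support that. Nor would masked testers make the comparison free of expectation effects, because participants know their arm and the walk is self-paced. Masking removes the tester's part only. The sample size is correct and unaffected.

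**What to change.** Amend Section 6.2 to say that:

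- participants and exercise trainers are not blinded;
- the Visit 2 6MWT and CPET are run, by rota from existing RMD staff, by someone who has not supervised that participant's exercise or education sessions, has not been told the allocation, and does not attend the Section 10.6 discussions of that participant before Visit 2;
- participants are asked not to disclose their arm, and the tester records whether the allocation became known;
- research image readings and interview transcripts are scored under the participant code, without arm.

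The cost is protocol wording and a scheduling constraint. Sample size, visits and the intervention do not change. The documents do not give RMD staffing numbers, so full masking may not be feasible. In that case the minimum rule is that a participant's own trainer does not run that participant's Visit 2 tests. Masking will be imperfect, which is why recorded unmasking is part of the change.

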6.3 STUDY INTERVENTION COMPLIANCE

We will monitor compliance and attendance with the exercise and education sessions, as well as adherence to the prescribed intensity and duration of exercise during the exercise training sessions in both groups, whether on-site at NIH CC or off-site (remotely). These include recording exercise heart rate, ratings of perceived exertion and number of exercise minutes in the exercise training log. For participants in the CON group, outcomes related to retention and feasibility such as number of exercise sessions conducted remotely, satisfaction with exercise and reason(s) for not participating in remote exercise sessions will also be captured.

7 STUDY INTERVENTION DISCONTINUATION AND PARTICIPANT DISCONTINUATION/WITHDRAWAL

7.1 DISCONTINUATION OF STUDY INTERVENTION

Participants in the AET+ arm who are unable to complete at least 80% of the exercise sessions, will be withdrawn from the study. If a clinically significant finding is identified (including, but not limited to changes from baseline) after enrollment, the investigator or qualified designee will determine if any change in participant management is needed. Any new clinically relevant finding will be reported as an adverse event (AE).

Participants are free to withdraw from participation in the study intervention at any time upon request.

An investigator may discontinue or withdraw a participant from the study intervention for the following reasons:

- Disease progression which requires discontinuation of the study intervention
- If any clinical adverse event (AE), laboratory abnormality, or other medical condition or situation occurs such that continued participation in the study would not be in the best interest of the participant
- Investigator discretion
- Positive pregnancy test

- Participant unable to perform exercise training for 2 consecutive weeks

7.2 PARTICIPANT DISCONTINUATION/WITHDRAWAL FROM THE STUDY

Prior to removal from the study, efforts will be made to have participants complete a safety visit within 14 days of the last exercise session.

Participants are free to withdraw from participation in the study at any time upon request.

An investigator may discontinue or withdraw a participant from the study for the following reasons:

- Significant study intervention non-compliance
- If the participant meets an exclusion criterion (either newly developed or not previously recognized) that precludes further study participation
- Concurrent enrollment in other interventional clinical trials
- Death
- Screen Failure

The reason for participant discontinuation or withdrawal from the study will be documented. Participants who sign the informed consent form and are randomized but do not receive the study intervention may be replaced. Participants who sign the informed consent form, and are randomized and receive the study intervention, and subsequently withdraw, or are withdrawn or discontinued from the study, will be replaced.

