5.2 EXCLUSION CRITERIA

An individual who meets any of the following criteria will be excluded from participation in this study:

1. Above normal performance (i.e., $\geq 100\%$ predicted) in the 6MWT based on normative data for gender and age ([94](#), [95](#))
2. History or cardiac condition as determined by NIH cardiology to be unsafe for exercise participation (e.g. ischemic heart disease, right- or left-sided heart failure, cor pulmonale or pulmonary hypertension, dilated or hypertrophic cardiomyopathy or non-idiopathic cardiomyopathy)
3. Significant hepatic or renal dysfunction
4. Cancer diagnosis with evidence of metastasis or a life expectancy of less than one year
5. History of stroke resulting in impairments in functional mobility that limits safe participation
6. Active substance abuse including EtOH
7. Severe psychiatric disease, not responsive to treatment or medication
8. History of diabetes *and* on insulin pump therapy, *or* uncontrolled diabetes with HbA1c $> 9.0\%$
9. Pregnancy
10. Acceptance onto a lung transplant waiting list
11. Extreme obesity with BMI $> 40 \text{ kg/m}^2$
12. On medications that would influence exercise performance such as beta blockers or antiretroviral therapy
13. Ongoing tobacco and/or nicotine product use
14. Enrolled in another interventional clinical research trial
15. Any other medical or health condition(s) that unduly increases the risk of exercise testing or training, affects the normal physiologic response to exercise testing or training, and/or would otherwise interfere with the ability to interpret the data as determined by the PI

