8.2.1 History and Physical Examination

A comprehensive clinical assessment will be performed by a credentialed NIH medical staff member. This exam will include vital sign measurements (e.g., temperature, pulse, respirations, blood pressure, oxygen saturation), anthropometric measurements (height and weight), detailed medical/social/surgical history, medication review, physical examination and other assessments (such as PEM assessment, balance/motor assessment, vision/hearing assessment and other functional abilities) as appropriate.

A brief physical exam at follow-up study visits will be performed by a credentialed RMD medical staff member to ensure continued inclusion and safe participation of the participants in the study.

Telehealth visits may also be performed by a credentialed and authorized NIH medical staff member, as necessary, for further review and follow-ups with the participant. All platforms utilized during the telehealth visit will meet all NIH information security requirements. During a telehealth visit, the credentialed NIH medical staff member will be in a closed and private environment to ensure privacy for the participant. The participant will be instructed to conduct the encounter in a private environment, free of distraction.

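### Section 7.2 lets unblinded staff withdraw and replace randomised participants for an exclusion found after randomisation, before the primary 6MWT is measured; such losses can differ by arm

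*Combined protocol and SAP*

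**What the plan says.** Section 7.2 lists the grounds on which an investigator may withdraw a participant from the study. One is: "If the participant meets an exclusion criterion (either newly developed or not previously recognized) that precludes further study participation". It has no time limit and does not require a decision made blind to arm. The same section says that participants who "are randomized and receive the study intervention, and subsequently withdraw, or are withdrawn or discontinued from the study, will be replaced"; those randomised but not yet treated may be replaced. Before removal it seeks only a safety visit, timed from the last exercise session. It does not ask for the Visit 2 walk test.

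Other sections bear on how this rule works:

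- **Blinding (6.2).** After randomisation, "due to the nature of exercise training and the time points involved in this study, the blinding process will no longer be possible".
- **Exercise sessions (6.1.1.2).** "Vital signs and review of cardiac-related signs or emerging symptoms will be performed before and after every session". On frequency: "The frequency of the sessions will be 3 times per week, unless make up sessions are needed in the 10 weeks".
- **CON before Visit 2 (1.3, 4.2, 6.1.1.1).** CON has weekly remote education. The schedule marks adverse-event review from Intervention Period 1 but leaves the vital-signs cell for that period blank.
- **Analysis set (9.3).** Only a per-protocol set is defined.
- **Recruitment (9.2).** It stays open until 38 participants in each arm have completed at least Visit 2.

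**The concern.** The randomised comparison is protected only while the people analysed are the people randomised. The 7.2 bullet removes a participant from the study, not merely from exercise, because of something learned after allocation by staff who know that allocation. The place is then refilled, and no analysis set brings the person back.

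If the chance of being removed depends on arm and is also related to how far the person would have walked at 10 weeks, the 38 per arm who remain are no longer comparable. Before Visit 2 the AET+ arm is looked at much more often than CON, so there is more opportunity in AET+ for a disqualifying condition to surface. If the people removed would have done worse than average, the AET+ mean is flattered.

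**Working it through.** **1. The plan's own figures reproduce.** Inputs from 9.2: gains of 77.4 m (SD 71.3) with exercise and 20.7 m (SD 98.6) in control, difference 56.7 m, alpha 0.05 (taken as two-sided), 80% power.

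- Standard error at 38 per arm = √(98.6²/38 + 71.3²/38) = √389.6 = 19.7 m. The noncentrality is 56.7/19.7 ≈ 2.87.
- Unequal-variance t-test power is 80.8% at 38 per arm and 79.7% at 37, so 38 is right.
- 76/0.85 = 89.4, rounded up to 90.

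The sample-size arithmetic is not at fault. The question is who ends up among the 38.

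**2. Path of a participant removed in week 5 (example).** Under 7.2 the person leaves the study and is replaced. Visit 2 does not take place, so there is no 10-week 6MWT. Under 9.2 the person does not count towards the 38, and under 9.3 no set includes them.

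**3. Opportunities for detection before Visit 2.**

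| | AET+ | CON |
|---|---|---|
| Exercise sessions with checks before and after | 3 × 10 = 30 | 0 |
| Weekly remote education contacts | 10 | 10 |
| Adverse-event review | yes | yes |
| Medication review, history and physical, cardiology, laboratory samples | none scheduled until Visit 2 | none scheduled until Visit 2 |

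The imbalance lies in the first row: vital signs, cardiac-related signs and symptoms, and (2.3.1.15) pain, tolerance and, in diabetes, glucose.

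**4. Size, as illustration only.** The documents give one overall completion figure (85%) and no withdrawal rate by arm or reason. Assume that the 38 retained in AET+ gain 77.4 m on average, those removed would have gained 0 m, and nobody is removed from CON.

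- 2 of 40 removed: mean had all been kept = 77.4 × 38/40 = 73.5 m; inflation 3.9 m.
- 4 of 42 removed: 77.4 × 38/42 = 70.0 m; inflation 7.4 m.

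Against the 30 m minimal important difference in section 3 these are 13% and 25%. Against the 56.7 m design effect they are 7% and 13%.

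**5. A second model.** Assume no true effect, removal of a share q from AET+ only, and a correlation ρ of 0.25 to 1 between removal and a poor change in 6MWT. Bias = ρ × 71.3 × φ(z_q)/(1 − q), with 38 analysed per arm.

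| q | Bias towards AET+ | Two-sided rejection rate (nominal 5%) |
|---|---|---|
| 2% | 0.9 to 3.5 m | 5.0 to 5.4% |
| 5% | 1.9 to 7.7 m | 5.1 to 6.8% |
| 10% | 3.5 to 13.9 m | 5.3 to 11.3% |

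If removal is unrelated to walking distance (ρ = 0), the bias is zero.

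**The case against.** The strongest reply is that the arm-dependent part may be small. Withdrawal is discretionary and limited to criteria that preclude further participation. Medication review, history and physical examination, cardiology review and laboratory samples fall at Visit 2 in both arms. CON is not unobserved: it has adverse-event review and weekly staff contact. Adverse events, laboratory abnormalities and disease progression are grounds in 7.1 for stopping the intervention, so worsening health does not automatically trigger the 7.2 bullet. All of this stands, and it limits the claim to losses that can differ. It does not remove the point: discretion exercised by unblinded staff, with no list of qualifying criteria, is itself a route to selective loss.

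Two stronger readings are tempting, and the documents support neither.

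- A reader might infer that new medication or nicotine use would be found mostly in AET+. No session check for either is scheduled, and the diabetes exclusion rests on insulin-pump therapy or HbA1c, not on a glucose reading at a session.
- A reader might infer that AET+ responders could be removed, because exclusion 1 is above-normal performance "in the 6MWT based on normative data for gender and age" and follow-up examinations are done "to ensure continued inclusion and safe participation of the participants in the study". Section 8.2 attaches that purpose to the physical examination, cardiac review, urine, blood and echocardiogram, never to the 6MWT. Sections 3 and 4.1 require the walk test after each regimen, and crossover for CON, with no performance gate. A distance recorded at Visit 2 would in any case already be available for the primary analysis.

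**Conclusion.** The point holds in a limited form. As written, 7.2 together with 9.2 and 9.3 allows unblinded, post-randomisation removal and replacement that costs primary outcomes. Monitoring before Visit 2 is heavier in AET+, so these losses can differ by arm. That they will differ is not shown.

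The size cannot be derived from the documents. The 3.9 m and 7.4 m figures rest on assumed counts, on zero gain in those removed, and on no removals from CON. With 2 to 5% removed from AET+ only, the false-positive rate moves little (5.0 to 6.8%). The problem becomes material only if removal is more frequent and strongly related to poor outcome.

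This route is separate from the 80% attendance rule in 7.1. Correcting that rule, or only adding an analysis set, would not recover walk distances that were never collected from people removed under 7.2. The change is worth making because it is specific and cheap.

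**What to change.** Replace the 7.2 bullet with wording such as:

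> Entry criteria determine eligibility at randomisation. A criterion that develops or is recognised later may lead medical staff to stop the intervention or particular procedures, but does not by itself end outcome collection. Visit 2 outcomes that medical staff judge safe, questionnaires and follow-up are still collected. The participant is analysed in the assigned arm and is not replaced. Withdrawals are reported by arm and reason.

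Three matching changes are needed:

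- **Section 9.3:** add an all-randomised analysis set. Otherwise analysis in the assigned arm contradicts the per-protocol definition.
- **Replacement sentence in 7.2 and recruitment rule in 9.2:** align both with no replacement. The 90 to be randomised already allow for 15% loss.
- **Pregnancy provisions:** 7.1 treats a positive test as a reason to stop the intervention, 8.2.3.1 makes a negative test a condition of continued participation, and 8.3.4.2 ends eligibility and further procedures. The new wording must be reconciled with these passages; the clinical rule is for the sponsor.

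**Cost:** protocol wording, a few extra Visit 2 assessments, and a slightly less favourable, more variable AET+ result. If all 90 (45 per arm) are measured and analysed with the SDs in 9.2, power for 56.7 m is 87.0%. It is 83.5%, 79.4% or 74.7% if the effect is diluted by 5%, 10% or 15%.
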